1.0 INTRODUCTION AND BACKGROUND

1.1 Introduction

The EndoRotor® Endoscopic Mucosal Resection System is a non-thermal mechanical endoscopic mucosal resection system for use in the gastrointestinal tract for benign neoplastic or pre-malignant tissue removal by interventional gastroenterologists and GI surgeons. The EndoRotor® System performs both tissue resection and extraction with a single device. The EndoRotor® System allows a gastroenterologist to access and remove polypoid or abnormal mucosa through an endoscope's instrument biopsy channel without removing and re-inserting the scope and without having to use multiple instruments. A motorized rotating cutting tool driven by an electronically controlled console performs tissue resection. Because the system automatically suctions and cuts about 1750 times a minute, resected tissue is immediately aspirated away from the resection site and collected onto a micron filter. Tissue collected on the filters can be used for pathological examination using standard methods.

Although the EndoRotor® was designed to be used within the esophagus, stomach, small and large intestine, in this study, Interscope will evaluate the use of the EndoRotor® to resect diseased colorectal mucosa only.

- In this study, recurrent flat or sessile lesions up to 6 cm in diameter and/or length in the appropriate patient will be removed using the EndoRotor[®].
- Various parameters, such as bleeding requiring intervention, perforation, speed of resection, and adequacy of the specimens to produce a diagnosis will be assessed. Routine endoscopic surveillance at 90 days will allow the endoscopist to assess adequacy of resection, the presence of persistent lesions and resection-associated stenosis.

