1.4.2 Summary of Pre-Clinical (Animal) Testing

Animal testing of the EndoRotor was conducted to evaluate the overall safety and performance of the device in an animal model. A summary of the study is presented below.

The objectives of this study were to evaluate the EndoRotor system for performance of tissue resection in an animal model, with respect to safety:

- Assessment of tissue response acutely and at 2 weeks post-resection utilizing standard light microscopy
- Clinical assessment of bleeding at sites of resection

The animal study was conducted under Good Laboratory Practice (GLP) guidelines. Six Yorkshire swine were utilized. Over 120 resections were completed between the colon, stomach, and esophagus, and distributed across different sizes. The studies were conducted at CBSET Lexington, Massachusetts, USA as part of a Good Lab Practices (GLP) protocol, as well as for a preliminary research project in Germany at the Institut für Nutztiergenetik, Mariensee, Friedrich-Loeffler-Institut (FLI) Bundesforschungsinstitut für Tiergesundheitusing in live pigs⁽⁵⁾.

Perforation and bleeding were the main safety criteria assessed. Other major endpoints were device performance/usability and histopathology. Perforation was noted in 2 (1.6%) of the resection sites, comparing favorably to the published rate of 2.3%. Bleeding was graded as mild (resolves in 2 minutes or less without intervention) in 79.5% of sites, as moderate bleeding (resolves in greater than 2 minutes without intervention) in 19.7% of sites, and one site (0.8% of sites) as severe bleeding (requires intervention to resolve the bleeding) which resolved after epinephrine administration. The bleeding rate that required intervention compares favorably to the rates for current interventional techniques published in the literature (0.8% vs. 1-16%). The study pathologist indicated that use of the EndoRotor® System for mucosal tissue resection in the porcine esophagus, stomach and colon was associated with favorable and clinically acceptable tissue responses. The EndoRotor® System received passing evaluation for all performance and intended use criteria by both physicians for the system usability assessment. Review of multiple techniques for the removal of polyps from the gastrointestinal tract suggests that the EndoRotor® System (with or without injection) will not introduce any new or unrecognized safety risks and will have a favorable risk/benefit profile.

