- For synchronous lesion interventions, respective lesion specimens should be isolated and separately collected to avoid confounding results.
- APC or similar techniques used for hemostasis on a resected lesion is not considered an alternative resection modality.
- Treat with EndoRotor, assess percentage of tissue removed with EndoRotor followed by photograph from region at equidistant location.
- Photo-document the region following EndoRotor treatment.
- If the complete lesion cannot be removed in a single treatment visit, a second visit can be scheduled to complete the removal in advance of the 90 day visit.

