5.7.1 Index Procedure Details

Refer to the Instructions for Use for a description of the procedure. The following data will be collected on all subjects during the index procedure and prior to discharge on the Index Procedure case report form:

- Summary of symptoms from physical examination
- Endoscopic imaging study
- The EndoRotor® achieved the attempted resection of the targeted lesion(s).
- The EndoRotor® pathological specimens were able to be interpreted by GI pathologists and enabled the rendering of clinical diagnoses.
- The total number of recurrent lesions treated with the EndoRotor.
- Time from scope insertion to scope removal.
- EndoRotor time from resection start to resection end.
- Adverse event assessment and treatment (i.e. delayed bleeding, presence of perforations). Note: Typical and routine steps (endoscopic clipping/mucosal apposition) will be taken to close perforations if they are discovered.
- Ease of use and overall satisfaction with the EndoRotor® System.
- Identification of technical difficulties and device malfunction, if any.
- Photographs post-EndoRotor treatment.

Current standard of care does not guarantee pathology in recurrent lesion procedures due to the difficulty to remove they often are treated with avulsion or Argon Plasma Coagulation. Since the EndoRotor retrieves specimen it can be sent for histopathological review. Although the EndoRotor is not intended for biopsy in this study pathologist will also be able to evaluate specimen that would normally be ablated. Resected tissue collected in the Specimen Trap will be placed in 10% Formalin and sent to the resident pathologist for histological evaluation. The

following steps will be taken for the review and interpretation of the specimens from the Specimen Trap following the procedure:

- 1. The resident pathologist shall be responsible for the preparation of the histology slides and the review and interpretation of the slides per hospital standard operating procedures.
- 2. The prepared specimen will be de-identified per hospital procedure and shipped by courier to an independent pathologist.
- 3. An independent pathologist selected by the Sponsor will prepare histology slides to assess the quality of the specimens.
- 4. The independent pathologist will document his/her assessment of the quality of the specimens.

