6.0 ADVERSE EVENTS

Adverse events will be recorded and documented throughout the duration of the study. In this study, adverse events related to the device or procedure, serious adverse events and Unanticipated Adverse Device Effects will be recorded. Adverse events (AE) unrelated to the device will not be documented on the CRF.

The Investigator at each participating center is ultimately responsible for reporting applicable adverse events to the Sponsor. The adverse event case report form (CRF) will be used to record

adverse event data. The adverse event CRF for a given visit must report all device-related and procedure-related adverse events that have occurred since the last documented visit.

The Sponsor shall review all adverse events for their severity, relationship to the study device(s) and comparative anticipated safety event rates. The Sponsor will conduct evaluations of any unanticipated device-related event per standard operating procedures.

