6.1.1 Serious Adverse Event (SAE)

A serious adverse event (SAE) is defined as an adverse event that:

- Is life threatening or fatal;
- Results in permanent impairment of a body structure or function;
- Results in congenital anomalies/birth defects
- Requires or prolongs hospitalization; or
- Requires medical or surgical intervention to preclude permanent impairment of a body function or permanent damage to a body structure.

Any other important medical event that may not result in death, be life threatening, or require hospitalization, may be considered a serious adverse experience when, based upon appropriate medical judgement, the event may jeopardize the subject or may require an intervention to prevent one of the outcomes listed above.

Delayed bleeding and perforations are the most serious adverse events associated with the resection of mucosal lesions, regardless of technique employed. Each requires the physician to identify it (the source of bleeding or the perforation) and swiftly act in a clinically appropriate manner to rectify the situation. Severe bleeding requires finding the source of bleeding and either using hemoclips or electrocautery to stop the flow of blood. Perforations, once identified

as such, can be treated using specialized endoscopic clips to approximate the edges and eliminate the perforation. Unidentified severe bleeding can result in anemia (decrease in the Hemoglobin and Hematocrit blood counts) with confusion, lethargy, and irritability, as well as hematemesis and hematochezia (bloody stools). Unidentified colon perforations can result in free air within the peritoneum causing compression of vascular structures (vena cava), abdominal distention, discomfort and pain, as well as sepsis and decreased cardiac output and death. Patients need to be made aware of the seriousness of not feeling well after resection of tissue and encouraged to immediately return to the hospital for evaluation.

NOTE: Planned hospitalization for a pre-existing condition or a procedure required by the study plan, without serious deterioration in health, is not considered a serious adverse event.

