12.0 LIST OF RELEVANT DEFINITIONS

Adverse Device Effect (ADE): An adverse device effect is defined as any untoward adverse event related to the use of an investigational device or unintended response to a medical device.

NOTE 1: This definition includes adverse events resulting from insufficient or inadequate Instructions for Use, deployment, implantation, installation, or operation, or any malfunction of the medical device. This definition includes any event resulting from insufficiencies or inadequacies in the Instructions for Use or the deployment of the device or any event that is a result of user error.

NOTE 2: This definition includes any event resulting from use error or from intentional misuse of the medical device.

Anemia: Decrease from baseline in red blood cells, hemoglobin, or total blood volume that is associated with hemodynamic changes or requires transfusion, or a drop in hematocrit to below 30%. Any documented anemic event requiring ≥ 2 units PRBCs will be considered an SAE.

Bleeding Complication at Index Procedure: Bleeding is considered an adverse event if additional measures such as endoscopic salvage methods (i.e. OTSC clipping, hemospray) or surgery become necessary.

Death: (divided into 2 categories)

- **A.** Cardiac death is death due to any of the following:
 - 1. Acute myocardial infarction.
 - 2. Cardiac perforation/pericardial tamponade.
 - 3. Arrhythmia or conduction abnormality.
 - 4. Stroke within 30 days of the procedure or stroke suspected of being related to the procedure.
 - 5. Death due to complication of the procedure, including bleeding, vascular repair, transfusion reaction, or bypass surgery.
 - 6. Any death for which a cardiac cause cannot be excluded.

B. Non-cardiac death is a death not due to cardiac causes (as defined immediately above).

Delayed Bleeding: Bleeding that occurs post-procedure requiring intervention.

Device Failure: A device that is used in accordance with the Instructions for Use, but does not perform according to the Instructions for Use and negatively impacts the treatment.

Device Malfunction: A malfunction of a device is an unexpected change to the device that is contradictory to the Instructions for Use and may or may not affect device performance. Includes damage, stress fracture or other failure as observed at the procedure.

Infection, systemic: Systemic infection documented by positive lab culture or clinical evidence, requiring medical treatment to treat and resolve.

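### The adverse-event threshold for bleeding at the index procedure is narrower than, or unclear against, the bleeding requiring intervention that Section 1.1 says will be assessed, and no other listed item clearly captures it

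*Combined protocol and SAP*

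**What the plan says.** Section 12.0 has two entries for bleeding. For the index procedure: "Bleeding is considered an adverse event if additional measures such as endoscopic salvage methods (i.e. OTSC clipping, hemospray) or surgery become necessary". For later bleeding: "Delayed Bleeding: Bleeding that occurs post-procedure requiring intervention".

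Section 1.1 sets out what the study will look at: "Various parameters, such as bleeding requiring intervention, perforation, speed of resection, and adequacy of the specimens to produce a diagnosis will be assessed". Section 1.4.2 uses the same kind of measure for the animal data, setting 0.8% of sites needing intervention against a published 1-16%.

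Hemostasis appears in two further places. Section 6.1.1, on serious adverse events, says: "Severe bleeding requires finding the source of bleeding and either using hemoclips or electrocautery to stop the flow of blood". Section 5.7 says: "APC or similar techniques used for hemostasis on a resected lesion is not considered an alternative resection modality".

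On data capture, the index-procedure list in Section 5.7.1 has the line "Adverse event assessment and treatment (i.e. delayed bleeding, presence of perforations" and no separate item for bleeding during the procedure or for the measure used to stop it. Section 6.0 states: "In this study, adverse events related to the device or procedure, serious adverse events and Unanticipated Adverse Device Effects will be recorded". Section 6.2.1 limits the adverse event form to related events that are serious.

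On reporting, the primary safety endpoint (4.1) is serious adverse events. None of the secondary endpoints (4.2) is bleeding, perforation or post-polypectomy syndrome. Section 8.5 mentions only the adjudication of serious events.

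**The concern.** Section 7.2 justifies the study partly by the wish to compare safety with other marketed devices. Sections 1.3.2 and 7.0 name bleeding, perforation and post-polypectomy syndrome as the main complications and give literature rates. A comparison on bleeding needs a count made at a known threshold.

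For the index procedure the threshold is worded around salvage methods and surgery. On the natural reading, routine hemostasis falls below it. If sites apply it that way, the study cannot produce the rate that Section 1.1 says will be assessed. Its index bleeding would then be counted more strictly than its own delayed bleeding and more strictly than the animal comparator. If some sites read it broadly and others narrowly, the pooled rate mixes two definitions. Section 8.7 pools over sites without testing for differences, so the mixture would not be noticed. The type of hemostasis may be hard to recover later if it is not captured at the time.

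**Working it through.** No figure in the plan has to be reproduced, because the point turns on wording. The places compare as follows.

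| Place | What makes bleeding count |
|---|---|
| 1.1 | Any intervention; type not limited |
| 12.0, delayed bleeding | Any intervention |
| 1.4.2, animal data | Any intervention; the one site counted was resolved with epinephrine |
| 12.0, index procedure | Additional measures, with salvage methods and surgery as the examples |

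**Step 1: is the index threshold narrower?** The first three rows agree. The fourth adds a qualifier and gives examples from the severe end. Ordinary hemoclips, cautery, argon plasma coagulation and epinephrine are neither named nor excluded. The threshold is therefore narrower on its natural reading and unclear on any reading.

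**Step 2: does another item capture the bleed?** The line in 5.7.1 covers adverse event assessment, so it collects an index bleed only if the bleed has already been classed as an adverse event. Its stated examples are delayed bleeding and perforation. Section 5.7 settles that argon plasma coagulation for hemostasis is not a resection modality, but not whether the bleed is recorded. Nothing else in 5.7.1 names hemostasis.

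**Step 3: if it is classed as a non-serious adverse event, is it recorded?** Under 6.0, yes, when related to device or procedure. Under 6.2.1, no. Section 11.1 has the independent adjudicator review related events as well as serious ones, which fits 6.0 but not 6.2.1.

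**Step 4: scale.** Inputs are n = 60 (5.4), the published 1-16% for bleeding requiring intervention (1.4.2), and 0-10.8% for bleeding after polypectomy, with no definition given (1.3.2, 7.0). Expected subjects = n x rate:

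- 60 x 0.01 = 0.6 and 60 x 0.16 = 9.6
- 60 x 0 = 0 and 60 x 0.108 = 6.5

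Exact (Clopper-Pearson) 95% limits for two illustrative counts:

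- 0 of 60: lower 0; upper = 1 - 0.025^(1/60) = 6.0%
- 6 of 60: lower = 2.5% quantile of Beta(6, 55) = 3.8%; upper = 97.5% quantile of Beta(7, 54) = 20.5%

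Counts of this order are possible within the plan's own ranges, so the choice of threshold can change the reported rate materially. This is not an estimate of the undercount. That would need the share of index bleeds controlled without salvage or surgery, which the documents do not give.

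**The case against.** The strongest reply is that Section 12.0 excludes nothing. It says if, not only if, and its list of measures is open-ended, so a hemoclip could be read as an additional measure. Section 6.1 leaves the evaluation of adverse experiences to the investigator's judgment. Bleeding that meets a serious criterion, such as hospitalization, is reportable whatever stopped it, and delayed bleeding counts at any intervention. A higher threshold at the index procedure may also be deliberate, since Section 6.1 sets aside events normally expected with endoscopy. Finally, Section 8.0 calls the analysis primarily descriptive, so named complication rates may look like extra endpoints.

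Most of this stands, and it rules out three stronger readings that a reader might infer:

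- **That bleeding stopped with hemoclips or cautery is definitely uncounted.** The text does not say so. It may go unrecorded, or be recorded at some sites and not others.
- **That bleeding called severe in 6.1.1 is not an adverse event.** The hemoclip and electrocautery sentence sits in a paragraph that opens with delayed bleeding and perforation, inside the section on serious events. Delayed bleeding is counted at any intervention.
- **That the reported rate would be some fixed fraction of 10.8%.** The documents do not say how that figure was defined or how it divides between index and delayed bleeding, and they give no share needing salvage or surgery. Only the 1-16% range is described as bleeding that required intervention.

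The reply does not remove the mismatch. An open-ended threshold is itself a source of variation between sites, and investigator judgment adds to it. A deliberate threshold for calling a bleed an adverse event still leaves Section 1.1 without the data it needs. Perforation and post-polypectomy syndrome are already assessed under 5.7.1 and 5.8, so reporting them adds table rows and no new assessment.

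**Conclusion.** The concern holds as a mismatch between definitions combined with a gap in data capture. The index-bleeding threshold in 12.0 is narrower than, or unclear against, 1.1, the delayed-bleeding entry and the animal comparator. No listed item clearly records index hemostasis, and 6.0 and 6.2.1 conflict on non-serious related events. As written, the plan does not reliably yield a rate of bleeding requiring intervention.

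The effect falls mainly on non-serious bleeding at the index procedure. The primary safety endpoint is little affected because it covers serious events. The size of any undercount is unknown; the 0-versus-6 contrast shows only that it could matter at n = 60. The conclusion assumes that at least some sites take the salvage-and-surgery examples as marking the level required.

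**What to change.** 1. On the index-procedure form, record for each lesion whether any hemostatic intervention was used and its type.
2. In 8.5, report descriptively in the Safety population, whatever the seriousness grade, the proportion of subjects with bleeding requiring any intervention (index and delayed shown separately), with perforation, and with post-polypectomy syndrome. Give each an exact interval; Section 8.4 already cites Clopper-Pearson, and a count per subject avoids clustering of lesions.
3. Reconcile 1.1, 5.7.1, 6.0, 6.1.1, 6.2.1 and 12.0, including whether non-serious related events go on the adverse event form.
4. If the Section 12.0 index threshold is deliberate, it can stay, provided the any-intervention rate is reported beside it. State which measures it includes.

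How bleeding is treated does not change. The cost is one form field, a few table rows and, probably, a less favourable reported bleeding rate.

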- ⁶ Pregnancy test for female subjects of child bearing potential within 1 day of procedure.
- ⁷ Second procedure can be completed if complete resection was not achieved during initial procedure
